2.3.2 Benefit Assessment

At randomization, participants have a 2/3 chance of being randomized to active IP (ASP0367). Participants randomized to placebo are unlikely to benefit from the double-blind treatment period of the study.

Additionally, enrollment in the study may be seen as an opportunity to contribute to the discovery of an effective drug for this highly unmet medical need.

2.3.3 Overall Risk-Benefit Conclusion

ASP0367 has the potential to address fatigue, exercise intolerance and muscle weakness and improve quality of life in participants with PMM. With appropriate precautions (e.g., cardiac monitoring), the potential risks mentioned above do not preclude initiation of a clinical study in PMM patients. This phase 2 study in participants with PMM will continue to evaluate the safety profile of ASP0367 and apply careful risk characterization and minimization activities.

The sponsor considers the overall benefit-risk to participants with PMM taking part in Study 0367-CL-1201 to be favorable.

3 OBJECTIVES, ENDPOINTS AND ESTIMANDS

The study objectives and endpoints are outlined in [Table 3].

Objectives	Endpoints	
Primary		
• To assess the dose response of ASP0367 on functional improvement relative to placebo	• Change from baseline in distance walked on the 6MWT at week 24	
• To assess the safety and tolerability of ASP0367 relative to placebo	 Safety and Tolerability through week 24 and end of study: Nature, frequency and severity of TEAEs Vital signs Weight 12-lead ECG Clinical laboratory tests (hematology, biochemistry [including serum cardiac troponin I] and urinalysis) C-SSRS 	
Secondary		
• To assess the dose response of ASP0367 on functional improvement and fatigue relative to placebo	• Change from baseline in Neuro-QoL Short Form Fatigue and Lower Extremity Function (Mobility) scores at week 24	
	• Change from baseline in time spent on the 5XSTS at week 24	
	Change from baseline in MFIS at week 24	
• To assess the effect of ASP0367 in overall	• PGIC scores at week 24	
participant functioning relative to placebo	• Change from baseline in PGIS scores at week 24	

Table 3Study Objectives and Endpoints

Objectives	Endpoints
Exploratory	 
• To assess the pharmacokinetics of ASP0367	 Plasma ASP0367: C_{trough} at weeks 12 and 24 and population pharmacokinetics
• To assess the exposure-response relationship of ASP0367	 Relationship between measured- and model-based pharmacokinetic exposure parameters (e.g., C_{trough}, C_{ave, ss}) of ASP0367 and endpoints of efficacy, safety and pharmacodynamic biomarkers, as appropriate
• To assess the effect of ASP0367 on lower extremity function relative to placebo	• Change from baseline in distance walked on the 6MWT at weeks 4 and 12
	• Change from baseline in minute-by-minute analyses (i.e., 6 th vs 1 st) of 6MWT at weeks 4, 12 and 24
	• Change from baseline in time spent on 5XSTS at weeks 4 and 12
	• Change from baseline in Neuro-QoL Short Form Fatigue score at weeks 4 and 12
	• Change from baseline in Neuro-QoL Short Form Lower Extremity Function (Mobility) score at weeks 4 and 12
	• Change from baseline in MFIS score at weeks 4 and 12
• To assess the effects of ASP0367 on quality	• PGIC scores at weeks 4 and 12
of movement and patient perception of change	• Change from baseline in PGIS scores at weeks 4 and 12
	• Change from baseline in EQ-VAS and EQ-5D-5L index at weeks 4, 12 and 24
• To assess the relationship between functional improvement and biochemical markers, as well as gene expression-based	• Change from baseline in the levels of serum and urinary biomarkers (serum FLNC, CYC, ALDOA and urinary TITIN) at weeks 12 and 24
pharmacodynamic biomarkers	 Relative change from baseline of whole blood PPARδ target gene expression levels at weeks 12 and 24[†]

Note: Placebo comparison will be up to 24 weeks and will not include open-label extension. 5XSTS: 5 Times Sit to Stand; 6MWT: 6-minute walk test; ALDOA: aldolase A; C_{ave, ss}: average plasma concentration at steady state; C-SSRS: Columbia-Suicide Severity Rating Scale; C_{trough}: concentration immediately prior to dosing at multiple dosing; CYC: cytochrome c; ECG: electrocardiogram; EQ-5D-5L: European Quality of Life 5-dimension, 5-level questionnaire; EQ-VAS: EuroQol visual analogue scale; FLNC: filamin-C; MFIS: Modified Fatigue Impact Scale; Neuro-QoL: Quality of Life in Neurological Disorders; PGIC: Patient Global Impression of Change; PGIS: Patient Global Impression of Severity; PPAR\delta: peroxisome proliferator-activated receptor delta; TEAE: treatment-emergent adverse event

†Blood samples will be collected and stored appropriately over the course of the study and then analyzed.

CCI

Estimands

Primary estimand will be defined by the following 5 attributes:

- Treatment: ASP0367 or placebo
- Population: Participants with PMM, as defined by the inclusion/exclusion criteria of the study.
- Endpoint: Change from baseline in distance walked on the 6-minute walk test (6MWT) at week 24.
- Intercurrent events and their corresponding strategies (see table below).
- Population level summary: Difference in change from baseline in distance walked on the 6MWT at week 24 between ASP0367 group and placebo group.

Intercurrent Events	Strategies to Handle Intercurrent Events
Treatment Discontinuation Due to Any Reason	For those participants who discontinued treatment, all observations after treatment discontinuation (Date of Last Study Drug Taken + 7 days) will be ignored. Analysis will be conducted assuming those participants remained assigned treatment and the condition that was observed before treatment discontinuation will continue, i.e., hypothetical strategy.
Study Discontinuation	For those participants who discontinued study, all observations after treatment discontinuation (Date of Last Study Drug Taken + 7 days) will be ignored. Analysis will be conducted assuming those participants remained assigned treatment and the condition that was observed before treatment discontinuation will continue, i.e., hypothetical strategy.
Prohibited Concomitant Treatment Use	For those participants who used the prohibited concomitant medication treatment, all observations will be included in the analysis, i.e., treatment policy strategy.

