9.4.3.2 Laboratory Assessments

For quantitative clinical laboratory measurements (hematology, biochemistry and urinalysis), descriptive statistics will be used to summarize results and change from baseline by treatment group and time point.

Laboratory data will be listed.

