6.5.2 Clinical Laboratory Evaluation

Quantitative values including hematology, biochemistry, and urinalysis will be summarized using mean, standard deviation, minimum, maximum and median by analysis group at each analysis visit. Additionally, a within-participant change will be calculated as the post-baseline measurement minus the baseline measurement and summarized in the same way.

Frequency tabulations of qualitative clinical laboratory variables (urinalysis) will be presented for each analysis group at each visit.

Additionally, amylase, lipase and troponin elevations above the ULN and 2xULN will be summarized by analysis group. The denominator for each criterion will be the number of participants who have at least one value after the day of first IP taken to 28 days after the last dose of IP for the double-blind treatment period of the study or moving to the OLE, whichever comes first.

The number and percentage of participants meeting the criteria during the defined period above will be summarized by analysis group.

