6.5.2.1 Liver Safety Assessment

The liver safety assessments will be summarized by the categories below based on the measurements from ALP, ALT, total bilirubin, AST and their combination. These parameters will be based on measurements from a local laboratory. If the baseline value is above ULN then use the baseline value instead of ULN.

- ALT > ULN, > 2xULN, > 3xULN, > 5xULN, > 10xULN, > 20xULN
- AST > ULN, > 2xULN, > 3xULN, > 5xULN, > 10xULN, > 20xULN
- ALT or AST > ULN, > 2xULN, > 3xULN, > 5xULN, > 10xULN, > 20xULN
- ALP > 1.5xULN, 2xULN, 2.5xULN
- Total Bilirubin > 2xULN
- (ALT or AST > 3xULN) and Total Bilirubin > 2xULN
- (ALT or AST > 3xULN) and ALP < 2xULN and Total Bilirubin > 2xULN

The last 2 criteria where 2 or more parameters are evaluated will be with the measurements on the same day or up to 1 day apart.

The denominator for each criterion will be the number of participants who have at least one value after the day of first dose taken to 28 days after the last dose of IP for the 52 weeks or moving to the OLE, whichever comes first. The number and percentage of participants meeting the criteria by 28 days after the last dose of IP for the 52 weeks or moving to the OLE will be summarized by analysis group.

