6.5.2 Clinical Laboratory Evaluation

Quantitative values including hematology, biochemistry, and urinalysis will be summarized using mean, standard deviation, minimum, maximum and median by analysis group at each analysis visit. Additionally, a within-participant change will be calculated as the post-baseline measurement minus the baseline measurement and summarized in the same way. Each laboratory result will be classified as low (L), normal (N), or high (H) at each visit according to the site supplied reference ranges. For the Placebo and ASP0367 groups, baseline values for CK-MM and CK-MB will be defined as the last non-missing observation prior to the first administration of ASP0367.

Frequency tabulations of qualitative clinical laboratory variables (urinalysis) will be presented for each analysis group at each visit.

Additionally, amylase, lipase and troponin elevations above the ULN and 2xULN will be summarized by analysis group. The denominator for each criterion will be the number of participants who have at least one value after the day of first ASP0367 taken to 28 days after the last dose of ASP0367. The number and percentage of participants meeting the criteria by 28 days after the last dose of ASP0367 will be summarized by analysis group.

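### The only SAP with a placebo group plans no low/normal/high classification or shift table, so about 33 of 42 blood parameters have no planned out-of-range count against placebo

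*Protocol*

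**What the plan says.** **Objective and endpoint.** Protocol section 3 (Table 3) sets the primary safety objective as "To assess the safety and tolerability of ASP0367 relative to placebo" and lists "Clinical laboratory tests (hematology, biochemistry [including serum cardiac troponin I] and urinalysis") among its endpoints.

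**Protocol analysis.** Section 9.4.3.2 says that "descriptive statistics will be used to summarize results and change from baseline by treatment group and time point", and that laboratory data will be listed. It mentions no out-of-range count.

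**52-week (double-blind) SAP.** Section 6.1 defines the 30 mg, 75 mg, any-dose and placebo groups. Section 6.5.2 plans the following: "Quantitative values including hematology, biochemistry, and urinalysis will be summarized using mean, standard deviation, minimum, maximum and median by analysis group at each analysis visit", with change from baseline handled the same way. Two further items follow there. Urinalysis results that are not numeric get frequency tables by group. For three kinds of blood marker the section plans a count: "Additionally, amylase, lipase and troponin elevations above the ULN and 2xULN will be summarized by analysis group".

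Section 6.5.2.1 adds liver threshold categories "based on the measurements from ALP, ALT, total bilirubin, AST and their combination". Section 6.5.1 defines a skeletal-muscle event of special interest that needs both a CK rise to at least 5 times ULN or baseline and a matching TEAE.

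**76-week SAP.** Section 6.5.2 contains a sentence that the 52-week SAP lacks: "Each laboratory result will be classified as low (L), normal (N), or high (H) at each visit". Under sections 4.1 and 6.1, its safety set is limited to participants in ASP0367 treatment, in two groups: ASP0367 any dose, and placebo switched to ASP0367.

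**The concern.** The endpoint is comparative, so the useful laboratory summary is how many participants in each arm leave the reference range, and in which direction. The sentence that would produce this sits in the plan without a concurrent control and is absent from the plan that has one. Both SAP versions are dated 9 July 2024 (section 7 of each), and neither explains the difference.

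The gap reaches markers that the protocol itself relies on. Section 2.3.1.3 treats heart and skeletal muscle toxicity as important potential risks. It names CK-MB among the cardiac markers, and CK, transaminases and LDH among the skeletal muscle markers. In the controlled SAP, CK-MB and LDH have no out-of-range count, and CK is counted only when the rise is large and has also been reported as a TEAE. If ASP0367 raised CK moderately, or moved creatinine or blood counts out of range in a few people, the planned tables would not show the rate on drug beside the rate on placebo.

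**Working it through.** No sample-size or error-rate figure is involved, so there is no stated number to reproduce. The check is a count of analytes and a side-by-side reading.

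**Step 1: denominator (Protocol Appendix 6, Table 10).** Hematology has 8 lines, with the white cell differential as one, and biochemistry has 34. 8 + 34 = 42 blood parameters. The 6 urinalysis lines are left out, because qualitative urinalysis is tabulated by arm.

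**Step 2: parameters with a planned count against placebo (52-week SAP).**
- Counted from 1 × ULN: ALT, AST, amylase, lipase, cTnI and cTnT (reading troponin as both) = 6.
- Counted only from a higher multiple: ALP (above 1.5 × ULN) and total bilirubin (above 2 × ULN). 6 + 2 = 8.
- Counted only at 5 times ULN or baseline, and only with a TEAE: CK. 8 + 1 = 9.

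**Step 3: what is left.**

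| Reading of covered | Covered | No planned count, of 42 | Biochemistry only, of 34 |
|---|---|---|---|
| Count from 1 × ULN | 6 | 42 − 6 = 36 (86%) | 34 − 6 = 28 (82%) |
| Any ULN multiple | 8 | 42 − 8 = 34 (81%) | 34 − 8 = 26 (76%) |
| Also CK with TEAE | 9 | 42 − 9 = 33 (79%) | 34 − 9 = 25 (74%) |

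All 8 hematology lines are uncovered under every reading. So are creatinine, cystatin C, sodium, potassium, glucose, lactate, LDH, CK-MB and CK-MM. Every planned blood threshold that defines an abnormality is an upper one, so no analyte has a count below the lower limit. A low platelet count or low potassium, for example, has none.

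**Step 4: can the 76-week SAP fill the gap?** No. Its section 6.8.1 uses, for participants randomized to placebo, only the baseline (week 52) and visits from the first ASP0367 dose onward. Their earlier placebo-period results are therefore not summarized there. The two active doses are also pooled. The sentence in its section 6.5.2 states a classification but specifies no table or shift analysis.

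**Step 5: can adverse events fill it?** Only in part. Protocol 7.2.1 asks investigators to record clinically significant changes as AEs, which is a judgement. Protocol 2.3.1.2 reports that amylase and lipase exceeded the reference range in a number of first-in-human participants and that none of these elevations became a TEAE. Out-of-range values and TEAE counts are therefore different quantities.

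**The case against.** **No commitment is broken.** Protocol 9.4.3.2 asks for descriptive statistics and listings, and the 52-week SAP delivers more than that. This stands: the SAP does not contradict the protocol, and a comparative objective does not by itself require shift tables.

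**A reader might infer that the trial can yield no out-of-range rate against placebo.** The documents do not support that. Laboratory data are listed, so counts can be derived later. Table formats sit in separate TLF specifications (SAP 6.1) that are not among the documents. What can be said is that the SAP text plans no such count.

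**A reader might infer that individual outliers would be invisible.** They would not. Minimum and maximum, for values and for change, are given by group and visit. What is missing is the number of participants out of range.

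**A reader might infer that a finished shift table was put in the wrong document.** The 76-week sentence is too thin for that; it could mean only listing flags.

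**The counts were targeted at earlier signals.** Amylase, lipase and troponin all appear in the earlier clinical findings in Protocol 2.3.1.2, so the selection looks deliberate. That is fair, but it does not explain leaving out CK-MB and LDH, or putting the TEAE condition on CK.

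**Other controlled routes exist.** TEAEs are tabulated by arm and severity, and the DSMB reviews safety laboratory data unblinded. These lower the stakes without giving a rate.

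**The study stopped for futility and the arms are small.** The 52-week SAP's revision table says several analyses were removed for that reason, without listing them. The 76-week SAP of the same date nevertheless keeps the classification. Sparse cells are a real limit on what the tables could show.

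**Conclusion.** The point holds as a gap in planned reporting for a primary safety endpoint, together with an unexplained difference between two SAPs of the same date. On the reading most generous to the plan, 33 of 42 blood parameters (79%) have no planned out-of-range count against placebo; on stricter readings it is 34 or 36. No analyte has a planned count below the lower limit.

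This rests on counting Table 10 lines as printed, reading troponin as both cTnI and cTnT, and taking the SAP text as the plan, since the TLF specifications are not available.

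It affects neither the efficacy analysis nor any error rate, and it does not show that a safety signal was missed. With efficacy stopped for futility, the controlled safety data are a main remaining product of the trial, so a low-cost improvement is worth making. Expectations should be modest: if the 33 interim participants split evenly (an assumption), each arm has 33/3 = 11, and one participant is 1/11 = 9 percentage points. At the planned 22 per arm it is 1/22 = 4.5 points.

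**What to change.** In 52-week SAP 6.5.2:

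1. Classify each quantitative result with a reference range as low, normal or high, and say which ranges apply. The 76-week SAP refers to site-supplied ranges, while both SAPs place safety laboratory testing in a central laboratory.
2. Tabulate the shift from baseline class to worst post-baseline class for 30 mg, 75 mg and placebo, with low and high directions shown separately. Do this through week 24 and over the whole double-blind part.
3. Include CK in these tables without the TEAE condition, and report CK at 5 times ULN or baseline both with and without a TEAE.
4. Show the number tested for CK-MB and CK-MM. Table 10 describes these as reflex tests triggered by the CK result, so their denominators will be selected.
5. State that the tables are descriptive.

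The cost is roughly one standard shift table per laboratory panel, from data already collected. The downside is more pages, sparse cells and some chance imbalances across many analytes in small arms. If the database has already been unblinded, label the tables as added afterwards and note the change in the CSR.

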4 STUDY DESIGN AND DOSE RATIONALE

4.1 Overall Study Design

This is a randomized, double-blind, placebo-controlled, oral dose, phase 2 study to evaluate the dose response of ASP0367 on functional improvement relative to placebo, safety and tolerability in participants with PMM. Efficacy (i.e., functional improvement) will be assessed by a functional motor test, 6MWT. The study consists of the following portions: screening (4 weeks); double-blind treatment period with 2 doses of ASP0367 vs matching placebo (24 weeks); and follow-up (4 weeks).

A 24-week treatment analysis of efficacy and safety will be the primary focus. Since participants enrolled in the study prior to implementation of Protocol Version 9.0 (Substantial Amendment 8), which removes the 52-week OLE period, may have a treatment duration of up to 76 weeks, a separate treatment analysis will also be conducted at later timepoints up to 76 weeks as per available data [Section 9]. An unblinded, independent Data and Safety

Monitoring Board (DSMB) will assess the overall safety and tolerability of ASP0367 throughout the course of the study as summarized in [Section 10.1.5.1.1].

Approximately 66 participants will be enrolled. At randomization, participants will be randomly placed into 1 of 3 arms (30 mg ASP0367, 75 mg ASP0367 or placebo; n = 22 for each arm) at a ratio of 1:1:1. Stratified randomization by site group (2 level: Mayo clinic_Minnesota; Non-Mayo clinic_Minnesota) will be applied.

At week 24 while enrollment continues, data from the first approximately 30 evaluable participants will be reviewed in an interim analysis, as described in [Section 9.6], to determine if the futility or efficacy stopping criteria are met while the study is ongoing. An Astellas internal DMC for interim analysis will assess the futility and efficacy of the study treatments and make recommendations about the ongoing conduct of the study as summarized in [Section 10.1.5.1.2]. An interim analysis of pharmacokinetic and pharmacodynamic data will also be reviewed by the DMC.

4.2 Scientific Rationale for Study Design

A randomized, placebo-controlled, parallel group design was chosen to detect changes in functional capacity and assess the safety/tolerability in PMM patients. Participants will be randomized to treatment to reduce selection bias, and further, both participants and the investigator will be blinded to treatment to reduce bias in the measurement of both safety and efficacy endpoints. Placebo was chosen as a comparator because there are no approved treatments for PMM.

The double-blind treatment period of the study will assess the dose response of ASP0367 on functional improvement relative to placebo to confirm that the appropriate dose level within the biologically active dose window is being selected with the new ASP0367 tablet formulation [Section 4.3] and assess the safety and tolerability of ASP0367 relative to placebo. A 6MWT will be employed as the primary efficacy endpoint, since exercise intolerance was one of the most key symptoms motivating PMM patients to participate in a clinical trial [Zolkipli-Cunningham et al, 2018] and the 6MWT is a sub-maximal exercise test used to assess functional capacity by measuring distance walked in six minutes. With the support of available nonclinical toxicity studies up to 52 weeks, 24 weeks randomized study duration for 6MWT has been chosen in considering disease progress.

As this current study is focusing on mitochondrial myopathies in which mitochondria are primarily involved, participants who demonstrate molecular genetic abnormality known to be associated with mitochondrial dysfunction will be enrolled in the study. Further, participant-reported symptoms (i.e., muscle weakness, fatigue and exercise intolerance) or physical examination findings of myopathy that are the predominant symptoms of the participant's mitochondrial disorder are required for the enrollment.

4.2.1 Summary of Changes to Study Design

The present study was originally designed as a randomized, double-blind, placebo-controlled, oral dose, adaptive phase 2/3 study with open-label extension (OLE) to evaluate the efficacy,

safety and tolerability of ASP0367 in participants with PMM. The original study design consisted of the following portions: screening (4 weeks); phase 2 dose selection portion with 2 doses of ASP0367 vs matching placebo (2 weeks); phase 3 portion with selected, single dose treatment vs placebo (up to 52 weeks); OLE (24 weeks); and follow-up (4 weeks).

Effective with implementation of Protocol Version 9.0 (Substantial Amendment 8), the original study design will be modified to become a phase 2 study (originally referred to as the "Phase 2 Portion") with a double-blind treatment period (24 weeks) and no OLE period. An interim analysis of approximately 30 evaluable participants who have reached week 24 of the double-blind treatment period will be conducted to evaluate futility and efficacy.

